### 11.3 POPULATIONS FOR ANALYSIS

An intent-to-treat (ITT) analysis set will include those who are enrolled in the Study regardless of adherence. All primary analyses will be conducted using the intent-to-treat analysis set.

### 11.4 DESCRIPTION OF STATISTICAL METHODS

#### 11.4.1 GENERAL APPROACH

This is a new statistical protocol to analyze how the use of the Sklip System enables laypersons to safely triage self-selected pigmented skin lesions of concern (PSLCs) from home with the same or better accuracy than pre-specified performance goals\* for detection of PSLCs that require biopsy and are malignant: **Melanoma and atypical melanocytic nevi with uncertain malignant potential** (moderate, severe, and high grade atypia; those with pathology reports that include notes such as: borderline, cannot exclude melanoma, cannot exclude early evolving melanoma, unusual features, atypical spitz nevi, suspicion for melanoma, re-excision (or further removal) should be considered or is recommended in the pathologist management comment) ( $\geq 95\%$  sensitivity,  $\geq 30\%$  specificity), **Squamous cell carcinoma** ( $\geq 80\%$  sensitivity,  $\geq 30\%$  specificity), **Basal cell carcinoma** ( $\geq 80\%$  sensitivity,  $\geq 30\%$  specificity).

\*Pre-specified performance goals have been reviewed with the FDA for testing the Sklip System (including SMSA) as a stand-alone device.

The Study protocol will also compare the accuracy of the Sklip System when used by a layperson (Participant) versus near-perfect Sklip System user (Study Coordinator), assess whether Sklip System improves triage of PSLCs  $< 6$  mm in diameter and triage of thin melanomas with  $< 0.8$  mm Breslow depth as suspicious, as compared to the current medical provider virtual triage method that relies on store-and-forward of smartphone clinical images (SCI), and assess accuracy of layperson-performed self-skin-exams (SSEs) at-home in the identification of all suspicious PSLCs present on their body as compared to the same layperson (Participant) evaluated with a full body skin examination (FBSE) by a dermatology Provider (DP) in-person.

The following method has been discussed with the FDA via Sklip Inc. Q-Submission Sprint Discussion (#Q211049/S002) to **establish the Study Ground Truth, described in the full IRB protocol**:

Dataset N) DDI dermoscopic diagnosis ground truth (DDI-GT) for PSLCs that were not biopsied during the In-Person Phase, and

Dataset O) Histologic diagnosis ground truth (H-GT) for lesions that were biopsied during the In-Person Phase

For Primary and Secondary endpoints below, the first SMSA output for each target PSLC will be used. If the first SMSA output for the target PSLC yields ERROR, then the second SMSA output for the same target PSLC will be used. If the first and the second SMSA outputs for the same target PSLC yield ERROR, then the third SMSA output for the same target PSLC will be used. If all three SMSA outputs yield ERROR, then the SMSA outputs for the target PSLC will be excluded. In other words, for each PSLC, there will be one SMSA output for analysis with a binary outcome “SUSPICIOUS” or “UNREMARKABLE.” Else, that target PSLC may be excluded from some analyses.

Descriptive statistics will be used to describe the demographic and clinical characteristics of the Study Participants. Categorical data will be summarized using counts and percentages; continuous data will be summarized using means and standard deviations. Underlying statistical assumptions will be checked with the analysis. We do not anticipate a need to transform any of the data; if assumptions are violated, then alternative methods will be considered.

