Packing the healthcare system can lead to delay of care for other patients: Layperson concern of unknowingly benign skin lesions can lead to overloading the healthcare system with unnecessary visits and increased delays for patients who may have an actual skin lesion that warrants biopsy, may be malignant, and ultimately requires equitable priority.

Interventional device: The Sklip System has been granted FDA Breakthrough Designation in 2021 (reported overall sensitivity of 94.47%) for its interpretation of DDI. The Sklip System will be made available to Study Participants via a non-commercial version of Sklip App with SMSA access via dedicated username and password (for research use only). The intended use of the Sklip System is stand-alone triage of PSLCs for skin cancer. Sklip System is intended for triage only (FDA Class 2). The Sklip System is not intended for diagnostic use (FDA Class 3). The reported Performance of SMSA for sensitivity of melanoma and atypical melanocytic nevi with uncertain malignant potential is 97.4%.

Study protocol intervention: We will test SMSA output from Participant-taken DDI of Participant-selected PSLCs in an at-home environment and evaluate real world performance of the Sklip System.

Potential intervention outcomes: The Sklip System may safely reduce submission of technically unclear images to DPs through its two-step SMSA algorithm. Use of the Sklip System requires a medical-device-assisted image (DDI) where the first step of the SMSA is to identify if the image is a DDI, then if the DDI is clear, in-focus and free of artifacts. If the DDI passes the first step, the SMSA then evaluates the uploaded DDI for presence of modified dermoscopy three-point checklist criteria. **The average time to obtain a Sklip System result is 5 seconds.** If positive, the lesion is flagged as SUSPICIOUS and information signals the Sklip System user to contact a healthcare Provider with urgency through clear product labelling in the Sklip Mole Analysis Report.

Hence, the Sklip System could potentially identify a malignancy with high sensitivity, safety and help prioritize layperson-to-patient triage pathway. Furthermore, for the purpose of access equity, the current publicly available commercial version of the Sklip App (since 03-2023) has a free-access map of every dermatology office location

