## 2. OBJECTIVES AND ENDPOINTS

### 2.1 PRIMARY OBJECTIVES AND ENDPOINTS

Primary Objective	Endpoint	Start	End
Sklip System enables laypersons to safely triage self-selected pigmented skin lesions of concern from home with the same or better accuracy than pre-specified performance goals* for	Using all Participant PSLCs recorded in the Participant Mole Log Sheets, triage accuracy measures of the SMSA output of Participant-taken DDI will be assessed using a 2x2 table,	First day of enrollment	Up to 42 days after first day of enrollment

detection of pigmented skin lesions that require biopsy:
 
Melanoma and atypical melanocytic nevi with uncertain malignant potential (moderate, severe, and high grade atypia; those with pathology reports that include notes such as: borderline, cannot exclude melanoma, cannot exclude early evolving melanoma, unusual features, atypical spitz nevi, suspicion for melanoma, re-excision (or further removal) should be considered or is recommended in the pathologist management comment): ≥95% sensitivity, ≥30% specificity
 
Squamous cell carcinoma: ≥80% sensitivity, ≥30% specificity
 
Basal cell carcinoma: ≥80% sensitivity, ≥30% specificity
 
*Pre-specified performance goals have been reviewed with the FDA for testing the Sklip System (including SMSA) as a stand-alone device.
	
where the SMSA rating of “SUSPICIOUS” or “UNREMARKABLE” will be estimated to pre-specified accuracy metrics discussed with the FDA.
 
The Sensitivity of the SMSA using Participant-taken DDI will be estimated to pre-specified performance goals described in sections above, using 0.05 significance level and 10% margin of error.
 
Triage accuracy measures of the Sklip System (specificity, negative predictive value, positive predictive value, and accuracy) will also be calculated.
 
The Ground Truth will be the combination of the following described in the Sections above:
 
Dataset N) DDI dermoscopic diagnosis ground truth (DDI-GT) for PSLCs that were not biopsied during the In-Person Phase, and
 
Dataset O) Histologic diagnosis ground truth (H-GT) for lesions that were biopsied during the In-Person Phase
		
---	--	--	--

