## 9. EFFICACY MEASURES

Assessment of any Participant self-selected PSLCs as part of the intervention in this Study will be conducted by the Sklip System. The Sklip System incorporates proprietary artificial intelligence (Ai) DDI analysis (SMSA) of PSLCs based on a modified dermoscopy Three-Point Checklist (MD3PC). PSLs presented to the SMSA are triaged into three categories: UNREMARKABLE, SUSPICIOUS or ERROR, and its performance has been verified and validated in alignment with expectations necessary for the safety and effectiveness of the device aligned with its intended use.

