#### 11.4.2 ANALYSIS OF PRIMARY ENDPOINT(S)

For the Primary Endpoints, the SMSA outputs of “SUSPICIOUS” or “UNREMARKABLE” from Participant-taken DDI will be compared to the Ground Truth, described in the Sections above. For **Melanoma and atypical melanocytic nevi with uncertain malignant potential** (moderate, severe, and high grade atypia; those with pathology reports that include notes such as: borderline, cannot exclude melanoma, cannot exclude early evolving melanoma, unusual features, atypical spitz nevi, suspicion for melanoma, re-excision (or further removal) should be considered or is recommended in the pathologist management comment), a 2x2 table consisting of the following counts (number of PSLCs):

- True Positives (TP): the SMSA output of SUSPICIOUS agrees with the Ground Truth for PSLCs that were

biopsied and were diagnosed as Melanoma or atypical melanocytic nevi with uncertain malignant potential, using Dataset (O) (Histologic diagnosis ground truth (H-GT)),

- False Positives (FP): the SMSA output of SUSPICIOUS does not agree with the benign Ground Truth using Dataset (N) (DDI dermoscopic diagnosis ground truth) and Dataset (O)
- False Negatives (FN): the SMSA output of UNREMARKABLE does not agree with the Ground Truth for PSLCs that were biopsied and diagnosed as Melanoma or atypical melanocytic nevi with uncertain malignant potential using Dataset (O)
- True Negatives (TN): the SMSA output of UNREMARKABLE agrees with the benign Ground Truth, using both Dataset (N) and Dataset (O)

For **Melanoma and atypical melanocytic nevi with uncertain malignant potential**, Sensitivity ( $TP \div (TP + FN)$ ) of the Sklip System will be calculated with a lower one-sided 95% confidence interval using the Exact (Clopper-Pearson) method. For **Squamous cell carcinoma** and for **Basal cell carcinoma**, Sensitivity and lower one-sided confidence intervals will be estimated in the same manner as for Melanoma and atypical melanocytic nevi with uncertain malignant potential.

Specificity ( $TN \div (FP + TN)$ ) will be the same for Melanoma and atypical melanocytic nevi with uncertain malignant potential, SCC, and BCC, where:

- False Positives (FP): the SMSA output of SUSPICIOUS does not agree with the benign Ground Truth, using Dataset (N) and Dataset (O)
- True Negatives (TN): the SMSA output of UNREMARKABLE agrees with the benign Ground Truth, using Dataset (N) and Dataset (O)

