### 11.5 HANDLING OF MISSING DATA

Missing data will not be imputed. Whenever possible, the analysis will be conducted using all available data. Missing data will be reported in the descriptive summary, and it will be noted if Participants were excluded from the analysis due to missing data.

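### Lesions with three ERROR outputs leave the primary 2x2, so at-home specificity is overstated by an unknown amount; no ERROR split by ground truth and no all-lesion analysis is planned

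*Combined protocol and SAP*

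**What the plan says.** Section 11.4.1 takes the first non-ERROR output among up to three attempts, and then: "If all three SMSA outputs yield ERROR, then the SMSA outputs for the target PSLC will be excluded". Shortly afterwards it is looser: "Else, that target PSLC may be excluded from some analyses". Those analyses are not named. The rule opens with "For Primary and Secondary endpoints below, the first SMSA output for each target PSLC will be used", although the current plan has primary and exploratory endpoints only, so its reach into the exploratory analyses is not stated.

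Section 11.4.2 defines all four cells of the table on SUSPICIOUS and UNREMARKABLE. A three-ERROR lesion therefore has no place in sensitivity, specificity, accuracy, PPV, NPV or prevalence.

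Three other places bear on the point:

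- The endpoint in section 2.1 begins "Using all Participant PSLCs recorded in the Participant Mole Log Sheets", though the same sentence then names only the two binary ratings.
- Section 9 treats ERROR as a device output: "PSLs presented to the SMSA are triaged into three categories: UNREMARKABLE, SUSPICIOUS or ERROR".
- Section 1.1 sets the purpose as testing the output "in an at-home environment and evaluate real world performance of the Sklip System".

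Sections 1.2 and 6.1.1 (ERROR labelling) direct a user with three failed attempts to see a healthcare provider in person. Section 6.1.1 also says that ERROR attempts are recorded up to the third. Section 11.5 adds: "Missing data will be reported in the descriptive summary".

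**The concern.** Failed scans are part of home use. A triage tool spares a visit for a benign lesion only if it returns UNREMARKABLE. After three ERRORs the label sends the user to a provider, the same practical outcome as a false positive, but the lesion drops out of the denominator instead. Reported specificity then answers a narrower question (how the algorithm performs once an image passes the quality gate) than the one the study sets itself (how the system performs at home).

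If ERROR is common among benign lesions, the planned figure could support the 30% specificity goal when the all-lesion figure would not. Nothing in section 11 would show which case applies, because neither an ERROR split by ground truth nor an analysis of all lesions is pre-specified.

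**Working it through.** **Inputs.** Section 11.2 plans 423 lesions: 1.96² × 0.974 × 0.026 / (0.10² × 0.023) = 422.98, which reproduces. Table 6 expects 220 lesions negative for malignancy, 107 of them non-suspicious: 107/220 = 48.6%, matching the 49% specificity in the text of 11.2. Table 4 uses 40% in its melanoma column. The goal is 30%. The bound is the one-sided 95% Clopper-Pearson lower limit of 11.4.2. The documents give no ERROR rate, so every rate below is an assumption.

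**Specificity, point estimate.** With *e* the ERROR share of benign lesions and ERROR scored as referral:

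all-lesion specificity = readable-image specificity × (1 − *e*)

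From 40%: 38% at *e* = 5%, 36% at 10%, 32% at 20%. It reaches 30% at *e* = 1 − 0.30/0.40 = 25%. From 48.6% it reaches 30% at 1 − 0.30/0.486 = about 38%.

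**Specificity, lower bound, 220 benign lesions.** True negatives = readable-image specificity × (220 − ERRORs), rounded. At least 78 true negatives out of 220 are needed for a bound of 30% (78 gives 30.1%, 77 gives 29.7%).

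| Readable-image specificity | ERRORs | Exclusion (planned) | Bound | ERROR as referral | Bound |
|---|---|---|---|---|---|
| 40% | 11 (5%) | 84/209 | 34.5% | 84/220 | 32.7% |
| 40% | 22 (10%) | 79/198 | 34.1% | 79/220 | 30.5% |
| 40% | 26 (11.8%) | 78/194 | 34.3% | 78/220 | 30.1% |
| 40% | 27 (12.3%) | 77/193 | 34.0% | 77/220 | 29.7% |
| 48.6% | 60 (27.3%) | 78/160 | 42.0% | 78/220 | 30.1% |
| 48.6% | 61 (27.7%) | 77/159 | 41.7% | 77/220 | 29.7% |

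At 30% readable-image specificity the bound is already 24.9% with no ERROR at all (66/220), so exclusion does not decide that case.

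**Sensitivity.** Under referral an ERROR on a malignant lesion counts as sent to a provider.

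- 52 carcinomas (Table 6), 95% sensitivity (Table 4), 4 ERRORs: exclusion gives 46/48 = 95.8%, referral 50/52 = 96.2%.
- Melanoma plus atypical nevi, 10 + 21 = 31 positives, 3 ERRORs, 27 of the 28 readable lesions flagged: exclusion gives 27/28 = 96.4%, referral 30/31 = 96.8%.

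Exclusion slightly understates sensitivity in both. Only if ERROR is scored as a miss does it fall (27/31 = 87.1%), and that is not the labelled action.

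**Can the rate be estimated?** Yes. As an illustration, 42 three-ERROR lesions out of 423 (9.9%) would have an exact two-sided 95% interval of 7.3% to 13.2%.

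**The case against.** The exclusion is a stated rule, not an oversight. The device has an image-quality gate before triage, and ERROR means that no assessment was made. Accuracy given a readable image is a legitimate, pre-specified quantity, and section 2.1 itself names only the two binary ratings. That stands: the planned analysis is valid for what it measures and should stay.

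It is also fair that the frequency of ERROR would probably be visible. Attempts are recorded, ERROR is a permitted value of Dataset C, and section 11.5 promises a descriptive account of missing data. What is absent is the split by ground truth and an analysis that uses it.

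Some lesions lie outside labelled use (certain anatomical sites, non-pigmented, nodular or very small lesions; Synopsis and 6.1.1). ERROR may be a correct rejection there, so these should not all count against specificity. The fix therefore separates them.

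Three stronger readings are tempting, and the documents do not support them.

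- *Exclusion hides missed cancers.* The label refers three-ERROR users to a provider, so sensitivity barely moves, and every participant is required to have a full body skin exam.
- *The rule breaches intent-to-treat.* Section 11.3 defines that set by participant and does not address lesions.
- *The specificity goal is in doubt.* That depends wholly on an unknown ERROR rate. At 10% ERROR, the bound stays above 30% at both 40% and 48.6% readable-image specificity (79/220, 30.5%; 96/220, 38.0%).

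**Conclusion.** The concern holds as a gap in what the plan will show about at-home use. Under the labelled action, exclusion overstates specificity by the factor 1/(1 − *e*) and leaves sensitivity almost unchanged. The direction follows from the documents; the size does not, because no ERROR rate is given.

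On the plan's expected counts, the conclusion against 30% changes only from about 12% ERROR among benign lesions if readable-image specificity is 40%, and only from about 28% if it is 48.6%. Setting the lower bound against the goal is the yardstick adopted here. The plan speaks of estimating accuracy to the goals and states no such test. The calculations treat lesions as independent, as the planned exact method does, and count every benign ERROR lesion as within labelled use.

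This should be fixed before analysis. Confidence is high that the analyses are missing, and no such confidence attaches to their impact.

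**What to change.** 1. Keep the planned primary analysis and label it *readable images*.
2. Replace the open wording in 11.4.1 ("Else, that target PSLC may be excluded from some analyses") with a list of the analyses that drop three-ERROR lesions, saying whether exploratory endpoints 1 to 3 are among them.
3. Pre-specify a 2x3 table of SUSPICIOUS, UNREMARKABLE and ERROR by ground truth, and the three-attempt ERROR rate with an exact confidence interval.
4. Pre-specify one all-lesion sensitivity analysis with ERROR scored as referral, following the label. Add ERROR scored as incorrect in both groups as a bounding case only.
5. Show lesions outside labelled use separately, and give the all-lesion result with and without them.
6. For unbiopsied lesions from the log sheets, Dataset N reads the participant's own dermoscopy image, which may be the one that the device rejected. Where the experts cannot read it, show the lesion as *ground truth unavailable* and bound specificity by treating such lesions as benign. This needs no additional expert reading and leaves unchanged the ground-truth method discussed with the FDA.

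The cost is SAP wording, a few more tables and a specificity figure that may be lower. No new participant procedure is needed, because the outputs and ERROR attempts are already to be recorded.

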#### 11.4.2 ANALYSIS OF PRIMARY ENDPOINT(S)

For the Primary Endpoints, the SMSA outputs of “SUSPICIOUS” or “UNREMARKABLE” from Participant-taken DDI will be compared to the Ground Truth, described in the Sections above. For **Melanoma and atypical melanocytic nevi with uncertain malignant potential** (moderate, severe, and high grade atypia; those with pathology reports that include notes such as: borderline, cannot exclude melanoma, cannot exclude early evolving melanoma, unusual features, atypical spitz nevi, suspicion for melanoma, re-excision (or further removal) should be considered or is recommended in the pathologist management comment), a 2x2 table consisting of the following counts (number of PSLCs):

- True Positives (TP): the SMSA output of SUSPICIOUS agrees with the Ground Truth for PSLCs that were

biopsied and were diagnosed as Melanoma or atypical melanocytic nevi with uncertain malignant potential, using Dataset (O) (Histologic diagnosis ground truth (H-GT)),

- False Positives (FP): the SMSA output of SUSPICIOUS does not agree with the benign Ground Truth using Dataset (N) (DDI dermoscopic diagnosis ground truth) and Dataset (O)
- False Negatives (FN): the SMSA output of UNREMARKABLE does not agree with the Ground Truth for PSLCs that were biopsied and diagnosed as Melanoma or atypical melanocytic nevi with uncertain malignant potential using Dataset (O)
- True Negatives (TN): the SMSA output of UNREMARKABLE agrees with the benign Ground Truth, using both Dataset (N) and Dataset (O)

For **Melanoma and atypical melanocytic nevi with uncertain malignant potential**, Sensitivity ( $TP \div (TP + FN)$ ) of the Sklip System will be calculated with a lower one-sided 95% confidence interval using the Exact (Clopper-Pearson) method. For **Squamous cell carcinoma** and for **Basal cell carcinoma**, Sensitivity and lower one-sided confidence intervals will be estimated in the same manner as for Melanoma and atypical melanocytic nevi with uncertain malignant potential.

Specificity ( $TN \div (FP + TN)$ ) will be the same for Melanoma and atypical melanocytic nevi with uncertain malignant potential, SCC, and BCC, where:

- False Positives (FP): the SMSA output of SUSPICIOUS does not agree with the benign Ground Truth, using Dataset (N) and Dataset (O)
- True Negatives (TN): the SMSA output of UNREMARKABLE agrees with the benign Ground Truth, using Dataset (N) and Dataset (O)

Specificity will be estimated with a lower one-sided 95% confidence interval using the Exact (Clopper-Pearson) method. Two-sided 95% confidence intervals for all Sensitivities and Specificities will also be calculated using the Exact (Clopper-Pearson) method.

We also will estimate the following measures of triage accuracy for each cutaneous disease entity with two-sided 95% confidence intervals using the Exact (Clopper-Pearson) method :

- $Accuracy (P) = (TP + TN) \div (TP + FP + FN + TN)$
- $Positive predictive value (PPV) = TP \div (TP + FP)$
- $Negative predictive value (NPV) = TN \div (FN + TN)$
- $Prevalence = (TP + FN) \div (TP + FP + FN + TN)$

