**Schedule for data collection:**

In order to avoid Participant PSLC recollection-bias, Study Coordinators will use the Participant Mole Log Sheet (PMLS) and Participant taken SCI/DDI for guidance and **record** the following Datasets in REDCap Cloud:

- A) Total number of PSLCs identified by the Participant at-home
- B) Total number of PSLCs identified by the DP in-office
- C) One (1) individual SMSA output recorded in the PMLS, per target PSLC (SUSPICIOUS, UNREMARKABLE and ERROR)

Ensuring that no PHI is shared, Study Coordinators will **export** the following from the Participant smartphone/tablet gallery titled “Moles” to the Study Site smartphone/tablet gallery via Bluetooth or secure email:

- D) One (1) Participant-taken SCI, per target PSLC
- E) One (1) Participant-taken DDI, per target PSLC
- F) One (1) Participant-taken SMSA output screenshot, per target PSLC

Then, Study Coordinators will **acquire** and **export** the following from the Study Site smartphone/tablet gallery to an OHSU secure cloud storage service:

- G) One (1) Study Coordinator-taken DDI (near-perfect image technical quality) for each PSLC recorded in the PMLS and suspicious PSLCs identified by the DP in-office that were not recorded in the PMLS

Then, Study Coordinators will **upload** the DDI in Dataset (G) to the SMSA on a Study Site smartphone/tablet and **record** the following Datasets into REDCap Cloud:

- H) One (1) Study Coordinator-taken SMSA output for each PSLC, recorded in the PMLS, using Dataset (G) (SUSPICIOUS, UNREMARKABLE and ERROR), including one (1) screenshots

Then, the Study Coordinator will **record** the following Datasets into REDCap Cloud:

- I) All other SCI of suspicious PSLCs identified by the DP in-office that were not recorded in the PMLS
- J) All other DDI of suspicious PSLCs identified by the DP in-office that were not recorded in the PMLS
- K) Pathology reports for all PSLCs that were biopsied during the In-Person Phase
- L) Number of adverse events reported during the Study

-----End of In-person Phase-----

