**Description of Satellite Study required activities**

Satellite Study Sites will also complete the above activities and securely **submit** their Datasets (A-L) to the Lead Study Site via OHSU secure cloud storage services. The Lead Study Site will prepare individual Qualtrics surveys using images from the Datasets above to create the following Datasets:

Dataset M) SCI triage decision (SCI-TD) based on Datasets (D) and (I), when at least two of three expert dermatologist readers have a concordant triage decision (MONITOR or BIOPSY). If there is a lack of concordance, an internationally recognized dermoscopy expert (dermatologist) will act as a fourth reader to determine the final SCI-TD

Dataset N) DDI dermoscopic diagnosis ground truth (DDI-GT) for PSLCs that were not biopsied during the In-Person Phase, using images available in Datasets (E) and (J), when at least two of three expert dermatologist readers have a concordant dermoscopic diagnosis. If there is a lack of concordance, an internationally recognized dermoscopy expert (dermatologist) will act as a fourth reader to determine the final DDI-GT

Dataset O) Histologic diagnosis ground truth (H-GT) for lesions that were biopsied during the In-Person Phase, based on evaluations using either physical or digital histologic slides (described in Sections below), when both independent expert dermatopathologists have a concordant histologic diagnosis. If there is a lack of concordance, a third internationally recognized expert dermatopathologist will determine the final H-GT.

The Study Sponsor will be responsible for Study costs (logistics, shipping, handling, research reading fees) associated with the use of either physical or digital histologic slides to create Dataset O. If digital histologic images (DHI) are chosen, the Lead Study Site will be asked to prepare DHI for their own Study Site Participants who received a biopsy during the In-person Phase. The Lead Study Site will have the option to prepare DHI for the Satellite Study Sites.

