## 5.3 MEASURES TO MINIMIZE BIAS

### 5.3.1 RANDOMIZATION/MASKING PROCEDURES

Blinding is considered unnecessary to reduce bias for all the observations because follow up evaluation for all Participants will follow standard clinical care pathways and is not affected by this interventional Study. The Study Site PIs and DPs will be fully blinded to all results of the At-home Phase, including the Participant Mole Log Sheet. Participants will be informed of the blinding activity prior to their FBSE to avoid DP selection-bias. Specifically, the dermatology provider will be instructed to say the following to each participant upon entering the patient room for the in-person FBSE: "Hello, my name is [name and title], the purpose of today's visit is to complete a full body skin examination as part of the at-home dermatoscopy study. To avoid bias, please hold with any questions related to your moles of concern until I have verified that I completed your full body skin examination and all other study related activities. I will be happy to address your questions or concerns at that time."

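### Section 11.4.2 gives an unbiopsied lesion that the expert panel diagnoses as melanoma, SCC or BCC no cell in the primary 2x2 table, so such lesions drop out of the primary result unreported

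*Combined protocol and SAP*

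**What the plan says.** Section 2.1 sets the scope of the primary endpoint: "Using all Participant PSLCs recorded in the Participant Mole Log Sheets". On the reference standard it states: "The Ground Truth will be the combination of the following described in the Sections above", namely Dataset N (expert-panel dermoscopic diagnosis) for lesions not biopsied and Dataset O (histology) for lesions that were. Section 11.4.1 and the synopsis repeat this combination. Nothing limits Dataset N to benign diagnoses.

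Section 11.4.2 then defines the four cells.

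- True positives are SUSPICIOUS lesions that were biopsied and are positive in Dataset O.
- A false negative is a case where "the SMSA output of UNREMARKABLE does not agree with the Ground Truth for PSLCs that were biopsied and diagnosed as Melanoma" or an atypical nevus, again from Dataset O.
- False positives are SUSPICIOUS lesions with a benign ground truth.
- A true negative is a case where "the SMSA output of UNREMARKABLE agrees with the benign Ground Truth, using both Dataset (N) and Dataset (O".

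SCC and BCC sensitivity is built in the same manner, and one specificity, based on benign lesions, serves all three entities. Accuracy, PPV, NPV and prevalence use the same four counts.

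Two passages bear on how often an unbiopsied lesion could be panel-positive. Section 8.1.2 makes biopsy optional, for lesions the provider finds suspicious. Section 9.2 requires definitive diagnosis of provider-verified suspicious lesions to be by biopsy.

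**The concern.** Dataset N can supply a malignant diagnosis, but the cell definitions can only use a benign one. A mole-log lesion that the provider passes over and the panel later calls melanoma, SCC or BCC has both an SMSA output and a reference diagnosis, yet it is counted nowhere. Sensitivity then becomes conditional on biopsy, which 2.1 does not say.

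If the SMSA called such a lesion UNREMARKABLE, it is a possible missed cancer, the event of most interest for a stand-alone home triage tool. If the SMSA called it SUSPICIOUS, it is a possible hit. Either would disappear without a reporting rule.

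Panel-read atypical nevi raise a related question. That entity is defined largely by histologic grade and pathology-report wording, and the plan does not define benign. An analyst could count such a lesion as benign, positive or excluded, and could make that choice after seeing the data.

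**Working it through.** **1. The plan's own figures.** Formula (1) in 11.2 gives 1.96² × 0.974 × 0.026 / (0.10² × 0.023) = 422.98, i.e. 423 lesions. Participants: 423 / 1.5 × 1.10 = 310.2, i.e. 310. Table 6 follows: 423 × 0.023 = 9.7 (10 melanomas); 413 × 0.05 = 20.7 (21 atypical nevi); 413 × 0.125 = 51.6 (52); 413 × 0.292 = 120.6 (121). All reproduce, and none depends on this point. Table 6 labels the 52 as BCC and the 121 as SCC, while the text of 11.2 lists 12.5% for SCC and 29.2% for BCC. The two entities are therefore named here by their counts.

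**2. Cell check.** Biopsy status, ground truth and SMSA output set against the definitions in 11.4.2:

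| Biopsied | Ground truth | SMSA output | Cell |
|---|---|---|---|
| yes | target entity (histology) | SUSPICIOUS | TP |
| yes | target entity (histology) | UNREMARKABLE | FN |
| either | benign | SUSPICIOUS | FP |
| either | benign | UNREMARKABLE | TN |
| no | melanoma, SCC or BCC (panel) | SUSPICIOUS | none |
| no | melanoma, SCC or BCC (panel) | UNREMARKABLE | none |

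The last two rows fail TP/FN because the lesion was not biopsied, and FP/TN because it is not benign. No other rule catches them. The exclusion in 11.4.1 is for lesions with three ERROR outputs, and 11.5 concerns missing data, whereas these lesions have both values.

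**3. Illustration.** The documents do not give the number of such lesions, so every omitted count below is an assumption. The bound is the one-sided 95% Clopper-Pearson lower limit for x of n, i.e. the 5th percentile of Beta(x, n − x + 1).

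Melanoma plus atypical nevi, goal 95%, 10 + 21 = 31 expected positives, one assumed miss:

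| Counted | Sensitivity | Lower bound |
|---|---|---|
| 30/31, as the plan counts | 96.8% | 85.6% |
| 30/32, one UNREMARKABLE lesion added | 93.8% | 81.6% |
| 31/32, one SUSPICIOUS lesion added | 96.9% | 86.0% |
| 31/31, no misses at all | 100% | 90.8% |

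A bound of 95% needs 59/59 (95.05%); 58/58 gives 94.97%.

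Entity with 52 positives, goal 80%, at Table 4's assumed 95% sensitivity (0.95 × 52 ≈ 49):

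| Counted | Sensitivity | Lower bound |
|---|---|---|
| 49/52 | 94.2% | 85.8% |
| 49/53, one omitted miss added | 92.5% | 83.6% |
| 49/54, two added | 90.7% | 81.5% |
| 49/55, three added | 89.1% | 79.6% |

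A single lesion changes the result only at the borderline count: 47/52 has a bound of 80.8%, 47/53 has 78.9%. For the entity with 121 positives, 115/121 has a bound of 90.4%, and it takes 13 added misses to fall below 80% (115/134: 79.9%).

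**The case against.** **Restricting TP and FN to histology looks deliberate.** The objective concerns lesions that need biopsy and are malignant, and Dataset N is used, in FP and TN. The entity tables are also not exhaustive by design: a biopsied SCC has no cell in the melanoma table. This stands as a reason to keep biopsy-confirmed sensitivity as primary. It does not close the gap, because the biopsied SCC is counted in its own table, while an unbiopsied panel-positive lesion is counted in none, and 2.1 does not disclose the restriction.

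**Such lesions should be rare.** Section 9.2 sends provider-verified suspicious lesions to biopsy. That makes them few, but it does not reach lesions the provider did not find suspicious, and the panel's response categories are not given.

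**The illustration mixes sources.** It takes totals from Table 6 and 95% sensitivity from Table 4, while Table 6's own split is 36/52 (69%) and 84/121 (69%) flagged. That is fair. The figures show how many lesions would matter; they are not a forecast.

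Three stronger readings are tempting and are not supported.

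- *That the omission inflates sensitivity.* The direction depends on the SMSA outputs of the dropped lesions. Section 5.3.1 states: "The Study Site PIs and DPs will be fully blinded to all results of the At-home Phase". The decision to biopsy should therefore not follow the SMSA output directly, and some panel diagnoses may themselves be reading errors.
- *That panel-read atypical nevi also clearly have no cell.* With a pathology-based definition and no definition of benign, their placement is ambiguous rather than missing.
- *That the panel reads the wrong image.* Section 3.1 has the panel diagnose from photographs "for PSLCs that were not biopsied during the In-Person Phase, using images available in Datasets (E) and (J", which for mole-log lesions means the participant's image, although a coordinator image (Dataset G) exists. This is a limitation: panel and SMSA may share image errors. It affects the measures built on FP and TN, not biopsy-confirmed sensitivity. Three assumed shared errors among the true negatives would move Table 6's specificity from 107/220 = 48.6% to 104/217 = 47.9%, against a 30% goal. Switching to Dataset G would move the shared-image problem to the coordinator comparisons in Exploratory endpoints 1 and 2, make the reference depend on re-identifying the lesion, and alter a method discussed with the FDA. It is not a clear improvement.

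**Conclusion.** The gap is real for melanoma, SCC and BCC, and follows from the wording of 11.4.2 alone. For atypical nevi the plan is ambiguous. The number of affected lesions and the net direction cannot be derived from the documents.

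On the assumed counts the effect is limited. For the 95% goal, one omitted lesion matters only if the point estimate is the criterion; the plan computes a lower bound but does not say which of the two is judged against the goal. With 31 positives the bound cannot reach 95% whatever happens to these lesions. For the 80% goals it takes three omitted misses at 49/52 or 13 at 115/121, unless the result is already borderline.

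It should still be fixed. A possible missed cancer should not leave the primary result without a trace, and the rule should be settled before outputs and panel readings are seen together.

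**What to change.** 1. In 11.4.2, keep biopsy-confirmed sensitivity as primary. Amend 2.1, and the matching synopsis text, to say that sensitivity is limited to biopsied lesions.
2. Pre-specify a supplementary analysis that counts an unbiopsied lesion with a panel diagnosis of melanoma, SCC or BCC as reference-positive for that entity: TP if SUSPICIOUS, FN if UNREMARKABLE. Report the number of these lesions and their SMSA outputs.
3. State that unbiopsied lesions the panel reads as atypical nevi are not counted in FP or TN, are reported separately, and are counted as positive in a sensitivity analysis.
4. Leave the panel's image source as it is. At most, note as a limitation that for unbiopsied mole-log lesions the panel reads the participant's image.

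The cost is wording and one extra table. All the data are already collected, and no image, reading or clinical procedure is added. The downside is that the supplementary analysis mixes photographic diagnoses with histology, so it must stay secondary and be labelled as such.
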